make 80% of all health care decisions for the family, shared the SSE brochure with relatives.^{4,6,29,30}

The *long-term goal* of this research is to reduce melanoma mortality by improving self-management of early detection of melanoma. Reduced mortality cannot be proven without effective structured melanoma SSE with partner assistance. One way to achieve partner-assisted SSE is to deliver a uniform self-management program to women who self-identify as at-risk, perform SSE and seek appointments with HCPs for concerning moles. In the absence of ready physician access due to COVID-19, we will test the feasibility of at-home mole self-sampling with a non-invasive adhesive patch used to acquire surface cells of the mole. Our *primary objective*, assessing effectiveness of a SSE education with partner assistance among at-risk women, extends the evidence-based SSE intervention developed among melanoma survivors and their skin check partners (R01CA154908)⁶ and delivers the program to women who had a screening mammogram, which demonstrated the individuals' commitment to health promotion and cancer screening.

STUDY ENDPOINTS:

Aim 1

Primary outcome:

Effectiveness of TMD with SSE will be defined as SSE performance. Further measures of fidelity will be assessed by:

- a) extent of body checked,
- b) recruitment of a skin check partner,
- c) time between noticing a concerning mole, requesting a mole self-sampling kit, and seeking HCP care for a concerning mole, and
- d) SSE sustained by monthly performance over 4 months.

Secondary Outcome:

The effect of TMD with SSE on seeking health care comparing intervention vs control groups for:

- a) inappropriate HCP appointments and skin biopsies for benign conditions, and
- b) appropriate HCP appointments for the clinical diagnosis of atypical (dysplastic nevus) or rule out melanoma and biopsy performed.

Exploratory Aim

Proof-of-concept Outcome:

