Subjects in the intervention arm will monitor new and concerning moles for 4 months by doing monthly skin checks and partner-assisted skin checks (if applicable), record the scores on a scorecard provided in their SSE brochure, and complete the monthly online survey, which asks about changes in mole scores and potential anxiety associated with evolving moles. Subjects will also receive a monthly text message to their personal phone with SSE reminders.

If the subject indicates on their monthly survey or by communicating with the study team, in the form of an email and/or call, that the score of their mole has increased, three options on how to proceed will be offered to the subject. The three choices are as follows: a) continue monthly checking the mole for change, b) receive the mole self-sampling kit to obtain genetic analysis to guide the decision to seek health care, or c) seek an appointment with an HCP.

The mole self-sampling kit contains the materials, directions and a Fed Express or USPS Express mail envelop to overnight the kit to the DermTech laboratory.

Participants may request a kit by email or telephone call to the research team, who will send the kit by Fed Express or USPS Express mail. Within 3-5 business days, the DermTech laboratory will provide the results of the gene analysis online to the PI, [name], who will inform the participant with a written report stating:

- a) the mole is benign, and nothing further is needed or
- b) the mole needs to be biopsied.

If the initial sample has too few cells for analysis, then the participant will be invited to obtain another sample, instructions will be reviewed by telephone or by Facetime with the participant and an additional sample will be obtained.

Participants requiring a skin biopsy will be referred to a local HCP. The research team will develop a participant navigation system for triage to a local HCP, including surgical oncologists, dermatologists, and family practitioners. This triage system will be used to refer participants to schedule an appointment for the skin biopsy within 2-3 weeks. The genetic analysis of the mole will be provided in a letter to the HCP selected by the participant.

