If the option to see the HCP is selected, the research team will assist with locating one and will remind the subject that the HCP may not be available for some time. The study team will not cover the cost of seeing the HCP or cost of treatment recommended by the HCP. The non-payments details are explicitly stated in the consent document.

If the mole(s) requires a biopsy and/or treatment, the EHR will be reviewed to identify diagnosis codes of the mole and review HCP notes.

If throughout the 4 months of active engagement in skin self-examinations, a participant in the intervention arm indicates that they found a concerning mole on their skin check partner while performing a partner skin exam, an opportunity for the concerning mole of the partner to be self-sampled will be offered. For the self-sampling to occur, the subject (the skin check partner) would first be asked eligibility questions to ensure they are over the age of 18 and meet basic eligibility criteria. Once eligibility is established, the partner will be sent an electronic consent form, via REDCap, and complete and sign the form,

indicating they understand what is expected of them as a research participant and the information that was presented to them in the consent document. The same process will be followed for the skin check partner as is in place for the research subject.

Controls (Group 1) will receive a healthy lifestyle brochure and a healthy lifestyle postcard after consenting online and completing baseline assessments. After enrolling in the study, a baseline survey will populate in REDCap, and the subject will be able to download a healthy lifestyle brochure and the postcard reminder. Upon request, the brochure will be mailed. Each month, the subject will receive an email to complete the monthly survey and will receive healthy lifestyle text messages to their mobile phone. The survey they receive will mirror the survey of the SSE intervention arm; therefore, awareness of SSE will be expected to increase, and SSE may be initiated among controls. If a subject indicates that they have found a concerning mole on their monthly survey, the subject will be advised to reach out to their health care provider for further assessment. After completing the final monthly survey, controls will be offered the SSE brochure.

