Design, Analysis, and Power Calculation with Target Enrollment Justification

For the RCT, participants will be randomly assigned to receive the SSE intervention or control (healthy lifestyle) in a 1:1 ratio. This will result in approximately 500 participants in each group. The primary analysis will be intent to treat, with data imputed one of two ways. First, we will run a “worse-case scenario” where all drop-outs will be assumed to not be performing SSE. Second, we will create 5 imputed data sets for missing data based on all available data and analyze with PROC MIANALYZE to obtain valid statistical inferences. From previous work, we expect at least 60% retention at 4 months.

We will use GLMM with a logit link to test if the intervention affects the rate of SSE, while adjusting for the repeated measures within individuals over the first 4 months. Using these repeated measures, and assuming an autocorrelation of 0.9, a total sample of 1000 would enable us to detect an increase from 80% of SSE in the control group to 86.3% in the intervention group. Assuming only 10% discordance, a sample of 500 control women provides 80% power to detect an increase of 7%, while the remaining 3% cease SSE. Additional fidelity measures in Aim 2 will be combined to score an overall standardized fidelity score at each time. If the mean fidelity score is 80%, a sample of 500 women provide enough information to produce a 95% Confidence interval with a width of 0.09. The sample for 500 intervention women provides 80% power to detect declining fidelity or sustainability of monthly SSEs as a standardized slope of 0.13. The secondary outcome of seeking HCP appointments for a necessary mole will be analyzed with generalized linear models, as described above, but considering the outcome as “any HCP appointment” during the study time frame. Previous data suggests that approximately 14% of women should contact HCP for an appointment, and our sample of 1000 women provides 80% power to detect a baseline rate in the control group as small as 21%.

Plans for securing the data is in the “provisions to protect the privacy interests of participants” section of the protocol.

PROVISIONS TO MONITOR THE DATA TO ENSURE THE SAFETY OF PARTICIPANTS:

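### The secondary outcome is defined as two components, inappropriate and appropriate care-seeking, but the stated analysis is one any-appointment indicator that does not compare the arms on both

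*Combined protocol and SAP*

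**What the plan says.** STUDY ENDPOINTS, Secondary Outcome, sets up a between-arm comparison: "The effect of TMD with SSE on seeking health care comparing intervention vs control groups for" two things. Component (a) is "inappropriate HCP appointments and skin biopsies for benign conditions, and" component (b) is "appropriate HCP appointments for the clinical diagnosis of atypical (dysplastic nevus) or rule out melanoma and biopsy performed".

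The only text on how this is analysed is in Design, Analysis, and Power Calculation with Target Enrollment Justification. It names the outcome and the method: "The secondary outcome of seeking HCP appointments for a necessary mole will be analyzed with generalized linear models". The rest of that sentence says how the outcome is to be coded: "as described above, but considering the outcome as “any HCP appointment” during the study time frame". One power statement follows. It takes about 14% of women as the proportion who should contact a provider and says that "our sample of 1000 women provides 80% power to detect a baseline rate in the control group as small as 21" per cent. It does not say which arm the 14% describes.

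The arms have different routes to care. Under STUDY INTERVENTIONS, an intervention participant whose mole score rises may, as one of three options, "receive the mole self-sampling kit to obtain genetic analysis to guide the decision to seek health care". Under PROCEDURES INVOLVED, a control who reports a concerning mole gets this instead: "the subject will be advised to reach out to their health care provider for further assessment".

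**The concern.** The outcome definition separates visits by whether they were warranted, and the analysis does not keep that separation. The labels inappropriate and appropriate imply that a fall in (a) and a rise in (b) would both be favourable, although the plan never states a direction. A single total moves down with the first and up with the second.

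The kit adds to the difficulty. It is meant to inform the decision to see a provider and is offered in one arm only, so total visits may differ between arms by design. If 14% is the intervention rate, the powered contrast is fewer visits under intervention. Without the split, such a result could mean that unneeded visits were avoided or that needed visits were missed.

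If the analysis is instead meant to cover only necessary-mole visits, the method for (a) is left to be chosen later, possibly after the data have been seen.

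**Working it through.** **Inputs.** From the Design, Analysis, and Power Calculation section: 14%, 21%, 1000 women, 80% power, 1:1 allocation with about 500 per arm. Alpha and sidedness are not stated for this comparison; two-sided 5% is assumed. The documents give no rates for (a) or (b), so every component rate below is assumed, with no woman having both visit types.

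**1. The plan's own figure.** For two proportions with n per arm and mean p̄:

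power = Φ[(|p₁ − p₂| − 1.96·s₀)/s₁], with s₀ = √(2p̄(1 − p̄)/n) and s₁ = √((p₁(1 − p₁) + p₂(1 − p₂))/n).

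- p₁ = 0.14, p₂ = 0.21, n = 500, p̄ = 0.175.
- s₀ = √(2 × 0.175 × 0.825/500) = 0.02403.
- s₁ = √((0.1204 + 0.1659)/500) = 0.02393.
- (0.07 − 1.96 × 0.02403)/0.02393 = 0.957, so power is 83.1%.

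The control rate detectable with 80% power against 14% is 20.7%, which rounds to the stated 21%. With a continuity correction, 490 per arm are needed and power at 500 is 80.9%. The figure reproduces, for one binary indicator.

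**2. The readings side by side.**

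| Reading of the analysis sentence | (a) | (b) |
|---|---|---|
| Any visit, warranted or not | pooled with (b) | pooled with (a) |
| At least one necessary-mole visit in the study period | no stated analysis | analysed approximately; the biopsy condition is not mentioned |
| Plural models means one model per component | analysed | analysed |

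The third reading would deliver the comparison. It fits poorly with the restriction to a necessary mole and with a single any-appointment indicator.

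**3. What the total can hide at the plan's own rates (hypothetical splits, 14% taken as the intervention rate).** Let controls have 14% (a) + 7% (b) = 21%.

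- Intervention 7% (a) + 7% (b) = 14%: only unneeded visits fell.
- Intervention 14% (a) + 0% (b) = 14%: only needed visits fell.

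Both give 21% versus 14% and the same 83% power. The second is a deliberate extreme. The indicator cannot tell them apart.

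**4. Cancellation under pooling (hypothetical, with a control total of 14% rather than the plan's 21%).**

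- Control 11% + 3% = 14%; intervention 9% + 5% = 14%. There is no difference in the total, so the rejection rate is 5%.
- Control 11% + 3% = 14%; intervention 6% + 5% = 11%. The pooled test has 30.0% power, while (a) alone, 11% versus 6%, has 81.0%.

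**5. What splitting buys, at 500 per arm (assumed rates).** The 95% CI half-width is 1.96·s₁.

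- 11% versus 9%: power 18.4%; half-width 1.96 × √((0.0979 + 0.0819)/500) = 3.7 points.
- 3% versus 5%: power about 36%; half-width 1.96 × √((0.0291 + 0.0475)/500) = 2.4 points.

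Splitting makes the result interpretable. It does not make modest shifts detectable.

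**The case against.** The best case for the plan starts from the sentence itself. The method described above it is a repeated-measures model over four months, so the change to any appointment may simply collapse monthly reports into one ever/never variable. On that view, any refers to time and not to visit type. The 14% supports this: PROCEDURES INVOLVED expects the same proportion, 140 of 1000, to identify a concerning mole, so it looks like a rate of need and not a sum of needed and unneeded visits. Nothing would then be pooled and nothing would cancel. This stands as a plausible reading, and it is why pooling cannot be asserted as the plan's intention. But it leaves (a) without a stated analysis.

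It can also be said that the endpoint section already prespecifies both comparisons, that the models could be fitted to each, and that a plan need not power every secondary component. The last point is right, and the missing power figure for (a) carries no weight here. What is missing is the analysis.

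Three stronger inferences are tempting and are not supported:

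- **That the trial would miss a real effect through cancellation.** The examples in step 4 rest on invented splits and do not use the plan's control rate. They show that cancellation is possible, not that it is likely or how large it would be.
- **That power is really the 74.2% obtained at 400 per arm,** from the 800 completers in PARTICIPANT POPULATIONS. That applies only if the outcome is lost with survey dropout. Visits are to be found by record review, and the documents do not say that this stops when surveys stop.
- **That visits without biopsy will not be abstracted,** because PROCEDURES INVOLVED mentions record review when a mole needs biopsy or treatment. It does not say only then, and the inclusion criteria and the privacy and health-information sections cover concerning-mole visits generally.

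**Conclusion.** The concern holds as a mismatch between a prespecified secondary comparison and its stated analysis. On the two natural readings, the any-appointment indicator either merges (a) with (b) or omits (a). The more generous reading, one model per component, is possible but is not what the sentence says.

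The consequence is one of interpretation, and its size cannot be put in numbers from the documents because they give no component rates. The plan's power figure is correct for what it covers, assuming a two-sided 5% test. A reader might infer that the power calculation is wrong or that the trial's main conclusion is at risk. Neither follows: the calculation reproduces, and the primary analysis of skin self-examination does not use this outcome. The point should be corrected before analysis.

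**What to change.** In the Design, Analysis, and Power Calculation section:

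- Replace the single indicator with two ever/never outcomes per woman, (a) and (b) as STUDY ENDPOINTS defines them. A woman with visits of both kinds counts once in each.
- Compare each by arm over all randomised women with a logit-link generalised linear model, and report the risk difference with its 95% CI.
- State before analysis whether benign in (a) is judged by clinical diagnosis or by pathology, so that one rule classifies every visit alike in both arms. This matters most for a rule-out-melanoma biopsy that proves benign, which could fall under either component. The sponsor should settle the boundary, since a rule supplied from outside could redefine the endpoint.
- Keep any appointment as a descriptive summary, attach the 14% versus 21% figure to it alone, and say which arm the 14% refers to.

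The cost is a reworded paragraph and one classification rule. Permission to use the records, visit notes, diagnosis codes and biopsy results are already planned. The drawback is precision: each component is rarer than the total, so (a) and (b) should be presented as estimates with confidence intervals and not as powered tests.

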Self-sampling kits will be sent to women who identify concerning moles and chose to perform self-sampling rather than watch the mole for change in a month. The blinded samples will be sent to DermTech, Inc., a CLIA laboratory, for analysis and the results reported directly to the PI. The PI will give the results to the participant, make a recommendation about the need to obtain a biopsy of the mole, offer to provide a referral to local HCPs, and send the laboratory results to the HCP selected by the participant. Anxiety/cancer worry will be assessed monthly to compare a) baseline measures, b) initial SSE and c) monitoring concerning moles for change.

Knowledge gained from this study may be helpful to other health care systems serving at-risk women and their families in locations with limited access to physicians, especially dermatologists.

BACKGROUND:

Early detection of melanoma remains a crucial component of effective treatment to reduce the mortality and morbidity of melanoma and the costs of melanoma care. In the United States (US), melanoma incidence has increased by 270% between 1973 and 2002 and is projected to continue rising in the US with doubling of newly diagnosed cases by 2030.^{1,2} Melanoma is the sixth most common cause of cancer in women in the US (fifth in men). There will be an estimated 100,350 new cases and 6,850 deaths in 2020.¹¹ Melanoma predominantly occurs in non-Hispanic Whites with a history of unprotected occupational or recreational sun exposure; however, indoor tanning by

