In order to complete this research before the end of the grant (March 2021), we need to have IRB approval in early May, which will allow EDW to build the lists of eligible subjects. Then we will enroll subjects remotely in June-August 2020 and follow them for 4 months with online surveys (Oct-Dec 2020). Finally, the EHR of HCP visits will be reviewed about 3-4 months after the completion of the last online survey. This additional period of EHR review (Feb 2021- March 2021) gives subjects time to obtain an appointment with their HCP and have a biopsy, if needed.

INCLUSION AND EXCLUSION CRITERIA:

Inclusion Criteria:

- Adult women (aged 18 and older) having a screening mammogram with no upper age limit, who had a screening mammogram from January 1, 2019 to February 28, 2020.
- Able to read English
- Vision enough to read a newspaper
- Self-perception of their potential melanoma risk
- Willing to perform SSE with a skin check partner
- Willing to complete monthly surveys for 4 months and receive monthly text messages to personal mobile phone
- Have home Internet access and smartphone with data plan
- Have access to Federal Express or US Postal Service Express Mail to send mole self-sampling kits
- Willing to allow the research team access to their electronic health record to abstract physician assessment of concerning moles, biopsy results and treatment
- Willing to provide up-to-date email address, mailing address and telephone number

Inclusion criteria of skin check partner to have mole self-sampled

- Male or female over the age of 18 years
- Able to read English
- Vision enough to read a newspaper

Exclusion criteria

- Women under the age of 18 years

- Women overburdened with other co-morbid diseases, medical treatments (e.g., chemotherapy), or cognitive impairment (e.g., by a stroke) as determined by the PI.
- Previous participation in SSE research previously which may be a confounding variable in data analysis

Exclusion criteria of skin check partner to have mole self-sampled

- Male or female under the age of 18
- Unable to read English

VULNERABLE POPULATIONS:

This study will not include the participation of vulnerable populations

PARTICIPANT POPULATIONS:

Accrual Number:	Category/ Group:	Consented: Maximum Number to be Consented or Reviewed/Collected /Screened	Enrolled: Number to Complete the Study or Needed to Address the Research Question
Northwestern Medicine: Prentice Women's Breast Center	Women ≥ 18 years old	500	400

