The research team will be permitted to access study-related, subject-reported information and the EHR of subjects who have a visit with a health care provider for a concerning mole. The EHR of skin check partners will not be accessed. The database that will house this data will only have de-identified data. A unique subject number will replace the use of names in the database. Our systems are guarded against outside entry by Northwestern's own firewall supporting 128-bit encryption. This level of encryption provides the highest level of protection against hackers, computer break-ins, etc. All data is de-identified. Only experienced research team members will work on this study and will have receive training that includes an emphasis upon the importance of confidentiality of information, and all personnel on the project will complete the required NIH training in the protection of human research participants. Physical copies of collected data forms will be retained in separate locked file cabinets and on computers with restricted and password-protected access, without links to the master code list. All data based on the research will be reported in aggregate form. No individual respondents will be identified. Electronic data will be maintained in a study-specific database on the server of the Department of Dermatology at the Feinberg School of Medicine. Paper-based files will be kept in a locked cabinet in a locked room within the Northwestern University Department of Dermatology research offices. Identifiable data will be kept separate from the case report forms and source documents. Data gathered as a result of this study are available to inspection on request by the Food and Drug Administration or other government regulatory agency auditors, and the Northwestern University Institutional Review Board (IRB).

Only approved research personnel will have access to the stored data. The PI is ultimately responsible for the receipt and transmission of the data. As per the Department of Dermatology protocol, data will be retained indefinitely after the completion of the study. All data and other information in this study will be maintained confidentially.

ECONOMIC BURDEN TO PARTICIPANTS:

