- Most recent mammography screening appointment information (date of screening mammogram and location of screening mammogram)

The EHR will be reviewed by the PI for:

- Health care provider notes from visit pertaining to a concerning mole (date of visit, notes from visit, diagnosis code of mole, plan of treatment and/or treatment)

HIPAA Authorization will not be obtained from skin check partners, as the study team will not be viewing their EHR.

QUALIFICATIONS TO CONDUCT RESEARCH AND RESOURCES AVAILABLE:

[name] has been a board-certified physician for over three decades and has conducted an NCI funded R01 and R21 of a similar nature. We will notify the Northwestern University IRB, our project officers, and NCI within 24-48 hours of any serious adverse event. All research assistants have CITI documents on file. Other resources. Lynn Sage Breast Center completes approximately 90,000 screening mammograms each year and Kishwaukee Hospital completes approximately 7,000 screening mammograms/year; therefore, there are adequate numbers of potential subjects to be identified by the EDW search. [name] has full-time research staff and voluntary medical students who fully support this research study at 100% effort. [name] also has weekly meetings with research staff to address any questions regarding the protocol, questions from research subjects, or study related procedures.

MULTI-SITE RESEARCH:

NA

REFERENCES

1. Guy GP, Jr., Thomas CC, Thompson T, et al. Vital signs: Melanoma incidence and mortality trends and projections - United States, 1982-2030. *MMWR Morb Mortal Wkly Rep.* 2015;64(21):591–596.
2. Global burden of disease cancer collaboration, Fitzmaurice C, et al. Global, Regional, and National Cancer Incidence, Mortality, Years of Life Lost, Years Lived With Disability, and Disability-Adjusted Life-Years for 29 Cancer Groups, 1990 to 2016: A Systematic Analysis for the Global Burden of Disease Study. *JAMA Oncol.* 2018;4(11):1553-1568.

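### The PI, who runs the intervention-only gene-result and referral pathway, is also the named EHR reviewer; nothing is masked to arm, and no rule separates appropriate from inappropriate visits

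*Combined protocol and SAP*

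**What the plan says.** Four parts of the protocol bear on this.

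- **Who reviews the record.** Protected Health Information: "The EHR will be reviewed by the PI for" provider notes from mole visits, including date, diagnosis code and treatment. The Inclusion Criteria also require each woman to be "Willing to allow the research team access to their electronic health record to abstract physician assessment of concerning moles, biopsy results and treatment". The privacy section adds: "The research team will be permitted to access study-related, subject-reported information and the EHR of subjects" who had a mole visit.
- **Who runs the gene-result pathway.** Objectives, Exploratory Aim: "The blinded samples will be sent to DermTech, Inc., a CLIA laboratory, for analysis and the results reported directly to the PI". After that, the PI will "make a recommendation about the need to obtain a biopsy of the mole", offer a referral, and "send the laboratory results to the HCP selected by the participant". Study Interventions describes a letter to the provider; Sharing Results with Participants describes a fax. Procedures Involved gives controls no kit and directs them to their own provider.
- **What is compared.** Study Endpoints, Secondary Outcome, compares the arms on two counts. The first, outcome (a), is "inappropriate HCP appointments and skin biopsies for benign conditions". The second, outcome (b), is "appropriate HCP appointments for the clinical diagnosis of atypical (dysplastic nevus) or rule out melanoma and biopsy performed".
- **What is analysed.** The power section sets the secondary outcome as any provider appointment during the study, fitted with generalized linear models.

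No section describes an abstractor masked to arm, a second reader, or a rule for assigning a visit to (a) or (b). The only blinding mentioned concerns personal identifiers on samples and kits.

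**The concern.** Outcome (a) is the only secondary outcome that would show whether the education leads to unneeded care. It has to be built from charts: someone selects the visits that concern a mole, then reads the notes, the code and any biopsy result. The named reader has already advised some of these women to have the biopsy whose appropriateness is in question, and those women are all in one arm.

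The categories leave room at the same place. If benign in (a) refers to pathology, a visit recorded as rule-out melanoma, with a biopsy that proves benign, meets both (a) and (b). A biopsy that follows a study letter and proves benign can land there. If such visits are sorted case by case by someone who knows the arm, any error can run in one direction and in one arm only. The between-arm result on unneeded care would then be hard to defend, whichever way it came out.

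**Working it through.** **1. The plan's own figure.** The power section gives 14% against 21% in controls, 1000 women, 80% power. Alpha is not stated; I assume two-sided 0.05 and 500 per arm.

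n per arm = [1.960 √(2p̄(1−p̄)) + 0.842 √(p₁(1−p₁) + p₂(1−p₂))]² / (p₁−p₂)², with p₁ = 0.14, p₂ = 0.21, p̄ = 0.175.

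= [1.960 √0.28875 + 0.842 √0.2863]² / 0.0049 = 462 per arm (924 in total). With continuity correction it is 490 per arm (980). Power at 500 per arm, uncorrected, is 83.1%. The figure reproduces. It concerns any appointment, so it needs no split into (a) and (b), and the present point does not change it.

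**2. Who knows the arm.** Only intervention women can use a kit, and every kit result goes to the PI. Knowledge of arm is therefore certain for enrolled kit users. Intervention women may instead keep watching the mole or go straight to a provider, and the protocol does not say whether the PI knows their arm.

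**3. Whether (a) and (b) exclude each other.**

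| Visit | Benign in (a) means clinical indication | Benign in (a) means pathology |
|---|---|---|
| Rule-out melanoma, biopsy benign | (b) only | (a) and (b) |
| Rule-out melanoma, biopsy atypical or melanoma | (b) only | (b) only |
| Benign indication, biopsy benign | (a) only | (a) only |

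The text does not choose between the readings. Aim 1 refers to both clinical and pathologic assessment. The PI's review list names no pathology, while the inclusion criteria include biopsy results in what the team abstracts.

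**4. Illustrative size.** The documents give neither a rate of inappropriate visits nor a misclassification rate. Assume both arms share a true rate q, 500 women per arm, and that a share f of the intervention arm's inappropriate visits is relabelled as appropriate. Then p₁ = q, p₂ = q(1−f), d = qf, and with p̄ the mean of p₁ and p₂:

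false-positive rate = Φ[(d − 1.96·SE₀)/SE₁] + Φ[(−d − 1.96·SE₀)/SE₁], where SE₀ = √(2p̄(1−p̄)/500) and SE₁ = √([p₁(1−p₁) + p₂(1−p₂)]/500).

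Example, q = 0.14 and f = 0.20: d = 0.028, SE₀ = 0.02099, SE₁ = 0.02097. The first argument is (0.028 − 0.04114)/0.02097 = −0.63, and the rate is 0.266.

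| q | f = 5% | f = 10% | f = 20% | f = 30% |
|---|---|---|---|---|
| 7% | 5.6% | 7.3% | 14.9% | 28.9% |
| 14% | 6.2% | 10.0% | 26.6% | 53.6% |
| 21% | 7.0% | 13.2% | 39.6% | 74.0% |

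At q = 14% there are 0.14 × 500 = 70 such women in the arm, so f = 10% and 20% mean 7 and 14 relabelled women. The 14% and 21% are borrowed from the plan only to set a scale. The plan uses 14% for women who find a concerning mole and for women who should contact a provider, which is not a count of inappropriate visits.

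**The case against.** The other side has substantial points, and several limit what can be said.

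- A reader might infer that the PI reviews the charts alone. The text does not say so. The inclusion criteria and the privacy section give the research team access and abstraction, and a data manager checks accuracy. This stands. It does not supply masking, though: the team sends kits, helps locate providers and meets the PI weekly.
- A reader might infer that the PI decides what is appropriate. No section says this. The categories draw on the treating provider's diagnosis and on whether a biopsy was done. This also stands. What is missing is the rule that turns those records into (a) or (b).
- A reader might infer that the PI is unblinded for every participant. Only kit users are certain.
- A reader might infer that every benign biopsy after a positive gene report falls in both categories. That holds only if pathology defines (a) and the provider recorded an atypical or rule-out-melanoma diagnosis.
- The only analysis specified for the secondary outcome uses any provider appointment and needs no split. This narrows the exposure a good deal. It does not answer the comparison listed under Study Endpoints, and choosing which visits concern a mole still takes some judgement.

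**Conclusion.** The point holds as a weakness in how one secondary comparison is assessed. An involved PI is the named EHR reviewer, arm is known for every enrolled kit user, nothing is masked, and the two visit categories can overlap with no tie-break. The comparison of appropriate and inappropriate visits is therefore open to arm-dependent classification.

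The documents do not show that misclassification will occur, how often, or in which direction. The error rates above rest on equal true rates in the arms, relabelling in the intervention arm only, 500 per arm with complete data, and two-sided 0.05. They show sensitivity and are not a forecast. The primary outcome, skin self-examination performance, is untouched, the analysis of any appointment is affected much less, and no sample size changes. This is an inexpensive improvement to make, not a fault that undermines the trial.

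**What to change.** Before the EHR review starts (it is the last stage in Study Timelines), amend Protected Health Information and Study Endpoints as follows.

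1. Existing research staff abstract, for both arms, the visit date, diagnosis code, provider's clinical indication, biopsy (yes/no) and pathology. The form carries no arm, gene result or study letter.
2. A person who did not do the abstraction classifies each visit from that form only.
3. The categories are mutually exclusive and fixed in advance. Atypical or rule-out-melanoma visits with benign pathology form their own category, reported by arm, and are not sorted into (a) or (b) case by case. Assigning them all to (a) on histology would relabel as inappropriate some visits that meet (b) as written.
4. Visits that followed a study gene letter are reported on a separate line.

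Cost: protocol wording, one form, and redaction for records with a mole-related visit. If the plan's percentages are taken as visit rates, which is an assumption, that is 0.14 × 1000 = 140 records, or 0.14 × 500 + 0.21 × 500 = 175. Masking will be incomplete where staff recognise a case, since they also handle kits and referrals, and some free-text detail is lost.
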